The primary aim of this study is to assess the effectiveness of rural pediatric obesity treatment delivered virtually to family homes (iAmHealthy) compared to an active attention control group (control). This is a cluster randomized design, with schools being assigned to condition (iAmHealthy or control) and the 8 parent/child pairs at each school being assigned to the same condition. Having children and families from the same school participate in the same mHealth group allows us to target the unique environmental characteristics that are both barriers to and facilitators of success in iAmHealthy.

II. Research Plan and Design

A. Design and Intervention.

The intervention is a cluster randomized design as groups will be randomized by school. Schools will be contacted via a flyer sent to all 550 rural elementary schools in the state of Kansas. Schools will contact researchers via a toll-free number and given detailed instructions on how to complete the required human subjects training and earn Institutional Review Board approval. Recruited schools will be stratified by two key variables (school size, percent free/reduced lunch) and then assigned to one of the intervention groups, such that all children/families who sign up at each elementary school will be assigned by school as a single group to either iAmHealthy or control (i.e., randomization occurs at the school level, not at the individual level). Any subsequent schools will be waitlisted for participation the next year.

Once 6 schools are randomized, they will be sent research grade scales and stadiometers and trained by research staff in all measurement and intervention procedures. At this time school representativeness will be analyzed each year, and if schools are not representative on either of the key metrics, schools recruited the following year will be oversampled in order that schools reach a representative sample by the end of the 5-year study.

The iAmHealthy family-based intervention provides behavioral, nutrition, and physical activity topics (see Table 4 and Appendix A). The intervention has an 8-week intensive weekly intervention phase followed by a 6-month period of

Table 4. iAmHealthy Standard Int	Rurally Tailored Topics	
Goal Setting & Sticker Charts	Reading Food Labels	Decreased focus on fast food
Stop Light Diet Parent Health Behavior Changes	Energy Balance Use of Privileges	Increased focus on eating at social gatherings

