Decreasing Sedentary/Increasing Physical Activity for Parents and Children Praising & Ignoring/ Making Healthy Choices	Family Exercise Ideas and Cooking with a Limited Budget Parties, Bar-B-Qs, and Eating Out	Increased information on exercise activities for children that can be done alone (due to poor proximity to neighbors, etc.)
Monitoring Screen Time	Nutrient Density	Increased attention to self- esteem
Portion Sizes/Healthy Foods in the Home	Self-Esteem	Tips for dressing appropriately for larger body types

monthly intervention sessions, for a total intervention period of 8 months (to coincide with the length of the typical school year).

Intervention groups will be delivered weekly to family homes at times that are convenient for participating families (typically evenings and weekends). If a participating family misses one group session, they will receive a makeup phone call. The 8 parent/child pairs from

each school will meet together via technology in a single cohort from their homes with intervention staff and meetings will last about one hour. The intervention focuses on behavioral, nutrition, and exercise topics, and contains both activities and didactic lessons. These topics are discussed at the individual, family and school/community level, allowing families to discuss barriers as well as facilitators unique to their rural schools and communities. The sessions begin with a review of progress since the last meeting, and end with parents and children setting goals. Parents and children will work together throughout each session, and both will be required to attend for the entire meeting.

Families will also be asked to complete their homework assignments with intervention staff via the iPad interactive televideo technology. This work will focus on goal setting, problem solving of barriers, reinforcement for tracking, and on completion of assigned homework assignments that are part of the manual. We will provide 11 hours of remote homework assistance to each family using the iPad interactive technology. We determined the 11 hour time period because 14 hours

of regular sessions plus 11 hours of homework assistance puts our intervention at the 25 hour threshold of contact hours set by the USPSTF (we will also have homework for each session, which will ensure that participants get the 25 hours recommended). The USPSTF suggests that

Table 5. Intervention Timeline (25 contact hours total per USPSTF guidelines).										

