	Weeks 1-8	Weeks 9-12	Weeks 13-16	Weeks 17-20	Weeks 21-24	Weeks 25-28	Weeks 29-32			
iAmHealthy Intervention	8 weekly sessions	1 session	1 session	1 session	1 session	1 session	1 session			
	11 hours of homework help via remote technology									

in the area of pediatric obesity treatment, children who receive at least 25 contact hours over a 6-8 month period are significantly more likely to be successful than children who receive fewer hours.²²

B. Sample Criteria

- 1. Sample Size:
 - a. About 144 parent/child pairs (8 or more parent/child pairs at 18 schools). Approximately 175 parent/child pairs will be consented to have 144 children go on to enrollment.
- 1. Inclusion/Exclusion Criteria:
 - a. Inclusion Criteria:
 - i. Family lives in a rural area (city and/or county population <20,000)
 - ii. Child BMI >85th and <99th percentile
 - iii. Child in 2nd thru 4th grade
 - iv. Both child and parent speak English
 - v. Family is available at times intervention is offered
 - b. Exclusion Criteria
 - i. Child has physical limitation or receives and injury which significantly limits physical activity
 - ii. Child has significant medical issue known to the school (i.e. cancer)
 - iii. Child and/or parents have a significant developmental delay or cognitive impairment that is known to the school

- iv. Child has a sibling already enrolled in the program
- v. Family moves to a non-participating school

C. Enrollment, Consent, and Procedures.

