Schools will send home letters to parents and families explaining the study and interested parents will be invited to call the researchers via a toll-free number with any questions. Parents will then come in for an orientation visit at the school and meet with the onsite school representative. In the event of school closure (ie. COVID-19 outbreak), these consenting sessions will take place remotely over the Zoom teleconferencing app instead of in person. At this meeting, the onsite school representative will go over the e-consent form with the parent and child. The e-consent will be housed in REDCap, and school study personnel will pull up the consent form on an iPad or a computer for the parent to review. The parent, child, and the onsite school representative will e-sign the consent form either with their finger or a mouse, depending on if they are using an iPad or a non-touch screen desktop computer. The consent form reads that a copy of the signed consent form will be mailed to them. KUMC study staff will print the signed consent form in REDCap and mail this form to the family once all the families in the school cohort have consented (which will be approximately a 1–2-week window). We will also have paper consent forms available in case of technology difficulties. Onsite school representative will only be permitted to use a paper consent process in the rare occurrence of internet or REDCap outage. If a paper consent is signed, a signed copy may be given to the parent at the time of consent. Paper consent forms would then be securely shipped to KUMC via FedEx express mail.

After parents and children are consented, the onsite school representative will measure height and weight and calculate BMI percentile for each child to assure that they qualify for the study. Schools will each recruit 8 target parent/child pairs. If they cannot recruit 8 parent/child pairs, the school will be waitlisted until such a time as they can. If more than 8 families express interest and complete enrollment procedures, if the school is assigned to iAmHealthy, those beyond the initial 8 will be offered a paper copy of the intervention manual to complete on their own and will not be enrolled as subjects (for the newsletter group, they will be sent the newsletter but will not be enrolled as subjects).

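### On the most direct reading, onsite staff can consent and screen families after they know their school's arm, and no step conceals the arm until enrolment is complete; the order should be stated and disclosure delayed.

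*Combined protocol and SAP*

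**What the plan says.** Schools are the unit of randomisation, stratified by size and by percent free/reduced lunch (II.A). Equipment and training come afterwards: "Once 6 schools are randomized, they will be sent research grade scales and stadiometers and trained by research staff in all measurement and intervention procedures". Measurement training and intervention training are thus one step.

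Recruitment is described in II.C. The school writes to families, and the onsite representative goes through consent with parent and child. Then: "After parents and children are consented, the onsite school representative will measure height and weight and calculate BMI percentile for each child". This is the eligibility check. II.D has fully trained representatives take height and weight on equipment the study provides.

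Other statements bear on the order:
- Before assignment, schools that make contact are "given detailed instructions on how to complete the required human subjects training and earn Institutional Review Board approval" (II.A).
- II.A also says that "all children/families who sign up at each elementary school will be assigned by school as a single group" to one arm or the other.
- "If they cannot recruit 8 parent/child pairs, the school will be waitlisted until such a time as they can" (II.C).
- Only the first eight families are enrolled; what later families receive depends on the school's arm (II.C).
- One inclusion criterion is "Family is available at times intervention is offered" (II.B).
- "Approximately 175 parent/child pairs will be consented to have 144 children go on to enrollment" (II.B).

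The documents do not say who holds the allocation, when representatives or families learn the arm, or whether the representative is kept unaware of it during recruitment.

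**The concern.** In a cluster trial, randomising schools protects the comparison of schools. It does not protect the choice of families within a school if the recruiter, or the families, know the arm when that choice is made. Enrolled families could then differ by arm in motivation or availability. Stratifying on two school-level variables does not address this, and the baseline covariate in II.E corrects it only in part. The intent-to-treat set in II.E starts from families who consent and complete all baseline measures, so it cannot restore anyone lost earlier.

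Some entry gates leave room for judgement. Live group sessions are described only for iAmHealthy, so availability at session times has an obvious meaning in one arm and an unclear one in the other. Two exclusions, for a significant medical issue and for developmental delay or cognitive impairment, depend on what the school is aware of. Response to the school's letter is voluntary. If the eight-pair waitlist rule operates after randomisation, it could also delay or remove a randomised school.

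**Working it through.** **Order of events.**
1. Equipment and measurement training arrive after randomisation, together with intervention training (II.A). A representative who has received them probably knows the arm.
2. The BMI eligibility check is done by that representative, after consent (II.C).
3. Height and weight are taken by trained representatives on study equipment (II.D).
4. Taken together, baseline measurement follows allocation, and the eligibility check appears to. The inference is weaker for the check: II.C names no equipment for it, II.D describes the outcome measure, and II.C places a measurement at the start of the intervention.
5. Consent needs neither scale nor stadiometer, and human subjects training comes before assignment, so consent could come earlier. No sentence says that it does.

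**Figures in the plan.** 8 × 18 = 144 reproduces. Expected loss between consent and enrolment: 175 − 144 = 31; 31/175 = 17.7%; 31/18 = 1.7 pairs per school. Consented per school: 175/18 = 9.7 for 8 places. The documents give no ICC, allocation ratio, effect size or power, so there is no power figure to reproduce.

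**Illustrative size of a shift.** Suppose d of the 31 losses are discretionary and the rest are objective and unrelated to prognosis. One arm loses its least favourable families on a prognostic trait; the other loses families at random. With q = d/(144 + d), the shift in the trait is φ(z_q)/(1 − q). An assumed trait-outcome correlation of 0.3 given baseline converts it to residual SD of the outcome.

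| Discretionary share | d | q | Trait shift (SD) | × 0.3 (residual SD) |
|---|---|---|---|---|
| None | 0 | 0 | 0 | 0 |
| Quarter | 7.75 | 0.051 | 0.111 | 0.033 |
| Half | 15.5 | 0.097 | 0.190 | 0.057 |
| All | 31 | 0.177 | 0.316 | 0.095 |

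**Effect on the test.** Assume 9 v 9 schools of 8, so 72 children per arm, and no true effect. Design effect = 1 + 7 × ICC; SE = √(2 × design effect/72). For ICC 0.01, 0.05 and 0.10 the design effects are 1.07, 1.35 and 1.70, and the SEs are 0.172, 0.194 and 0.217 residual SD. Two-sided 5% test, noncentral t on 16 df:

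| Shift (residual SD) | ICC 0.01 | ICC 0.05 | ICC 0.10 |
|---|---|---|---|
| 0.033 | 5.4% | 5.3% | 5.2% |
| 0.057 | 6.1% | 5.9% | 5.7% |
| 0.1 | 8.5% | 7.7% | 7.2% |

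The last row is close to the case in which every loss is discretionary (0.095). These rows are not bounds: they assume perfect selection on the trait, and they leave out who volunteers before consent.

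**The case against.** The strongest reply is that the text may mean recruitment first. Families who sign up are then assigned as a group. Human subjects training precedes assignment. The waitlist rule reads naturally as an entry condition, since II.A uses the same term for schools held over to the next year. The rule for families beyond eight applies to those who have completed enrolment procedures, which fits disclosure after enrolment. All of this stands as a possible reading, and a reader should not infer that randomisation certainly precedes recruitment. But no sentence confirms the benign order, and II.A as written supplies the measuring equipment only afterwards.

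Second, discretion is limited. Taking the first eight restricts choice among volunteers; grade, residence, language, enrolled sibling and BMI are largely objective; and BMI failure or being surplus to eight can explain many of the 31 losses. This stands too. It does not limit who answers the letter, who is judged available, or who is excluded on the school's knowledge. The availability criterion is written once for all families and sessions are timed to suit them, so different use by arm is a possibility, not something the documents state.

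Third, consent pages were removed, so what families were told cannot be checked, and it should not be inferred that they knew their arm. This does not explain the silence about the representative.

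Finally, much larger distortions can be constructed, such as a 0.63 SD trait shift (2 × 0.316) if every loss is discretionary and the arms select in opposite directions. Even that gives only 0.189 residual SD at a correlation of 0.3. The documents do not support using such a case as an estimate.

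**Conclusion.** The point holds as a weakness in how recruitment is sequenced and described. It is not evidence that the arms differ. Followed as written, the plan lets the person who consents and screens know the arm, and nothing prevents it. Confidence is medium because the order is pieced together from three sections. If sign-up and screening do come first, the risk is small and one sentence would show it.

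The magnitude is unknown. The range runs from no effect, through false-positive rates of about 5.2-6.1% for shifts of 0.03 to 0.06 residual SD, to 7.2-8.5% at 0.1 SD. It rests on assumed values for the discretionary share, the trait-outcome correlation, the ICC and equal allocation. The change is worth making because it is cheap and removes a doubt that no analysis could remove later.

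**What to change.** In II.A and II.C, for schools not yet randomised:
1. Send equipment and train in consent and measurement first.
2. Complete sign-up, consent and eligibility screening, judging availability against the same stated session times in every school.
3. Apply the eight-pair waitlist rule and lock the roster in REDCap.
4. Only then disclose the arm, or randomise within the existing strata, and give intervention training.

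State who knows the arm at each step. If this is already the practice, correct the sequence in II.A to say so.

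For all schools, report by arm the schools randomised and waitlisted, and the families approached, consented, ineligible (with reason), surplus to eight, and enrolled.

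Cost: no extra participants. Training is given in two steps, some equipment goes to schools that fall short of eight pairs, and schools learn their arm about 1-2 weeks later (the consent window in II.C), in a programme tied to the school year. The version is dated August 2020, so few schools may be left to benefit. If six schools per round is right, there are 18/6 = 3 rounds, and each round not yet randomised covers 6 × 8 = 48 of 144 pairs. Stating the order and reporting the counts costs almost nothing and applies to every school.

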Following completion of all baseline measures (which will take one hour; see Measures below), iAmHealthy families will receive their technology devices via postal service and will be scheduled for a 30-minute phone orientation session to all technology. Intervention components will then be implemented for iAmHealthy or newsletter. Weight and height measurements will be taken at each child's school at the start of the intervention and monthly throughout the intervention period for both parents and children by onsite trained staff. Parents or children may have their weight taken at a local hospital or clinic if a medical specialty scale is needed, such as a wheelchair scale or a high-capacity scale. In the event schools are closed (ie. COVID-19 outbreak), parents will be trained on how to obtain height and weight at home. Digital scales and tape measures will be sent to the families, and each family will measure the height and weight during a video call via Zoom app with an iAmHealthy team member to ensure measurement accuracy. At the completion of the intervention (8 months later), the second one-hour measures collection will take place. Sixteen months following the end of the intervention, the third one-hour measures collection will take place (20-month follow-up).

Families from the intervention/control study will be paid proportionally for completion of measures as is required by our local IRB (\$80 at baseline, 8 months, and 20 months, plus \$100 for monthly heights and weights over 10 time points). Participants who wear the activity monitors for at least 7 days will receive an extra \$20 at baseline, 8 months, and 20 months. Altogether, families may receive up to \$400. A payment timeline for participants is attached below:

	Start of Study	1 Month	2 Month	3 Month	4 Month	5 Month	6 Month	7 Month	8 Month	20 Month	Total for Study Completion
Online Surveys	\$80								\$80	\$80	

Height & Weight	\$10	\$10	\$10	\$10	\$10	\$10	\$10	\$10	\$10	\$10	
Activity Monitors	\$20								\$20	\$20	
Total	\$110	\$10	\$10	\$10	\$10	\$10	\$10	\$10	\$110	\$110	\$400

In case of activity monitor malfunction, we would like to be able to offer an additional \$20 for the participant to wear the device again. Thus, a participant could earn over \$400 if they are asked to wear the monitor a 2nd time.

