- 2. Child Body Mass Index z score (BMIz) and Parent Body Mass Index (BMI). To calculate child BMIzand parent BMI we will use standard formulas/equations. Height and weight will be assessed by fully trained onsite school representatives on standardized, calibrated equipment provided by the study. All staff will be trained in standard research anthropometric measurement protocol, including calibration techniques. Standing height will be assessed in

Table 6. Measures timeline.			
Primary Outcome Measures	Baseline	8 months	24 months
24 hour food recall (child)	Х	Х	Х
Physical Activity Monitors (child)	Х	Х	Х
Child BMIz/ Parent BMI ¹	Х	X	Х
R each			
Participation	Х	Х	
Structured Interviews with Non- participants		Х	
E fficacy			
HRQOL (parent, child)	Х	Х	Х
Parent Distress (parent)	Х	Х	Х
Peer Victimization (child)	X	Х	X
Child Depression (child)	Х	Х	х
Satisfaction (parent, child)		х	
Stigma (parent, child)		Х	
A doption			
Assess Representativeness of Participating Schools	Х		
I mplementation			
Attendance/Participation		Х	
Cost		Х	
Group Process		Х	
M aintenance			
Structured Interviews With Participating Schools		Х	
Other Measures			
Demographics (parent)	Х		
Food Insecurity	Х		
Post Questionnaire (parent)		Х	
Technology Feasibility (parent)	Х	Х	
$^{1}\mbox{Child BMIZ/Parent BMI will be taken monthly throughout}$	the 8 month into	ervention period	

triplicate via a Harpenden Holtain stadiometer, Model 603 (Holtain, Crymych, UK). Weight will be measured in triplicate on a portable SECA digital scale (SECA, Hamburg, Germany) after the participant has been asked to void. Parents and children will be measured with light clothing and no shoes.

Other Measures

1. *Demographics*. This questionnaire will ask about age, race, ethnicity, income, free/reduced lunch status, and parental education. We will also assess for the availability of home computers, high-speed internet access, tablets, smartphones, or other technology already present in the home that could be utilized for secure videoconference

- connections in future studies.

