Some outcomes will be analyzed using the multilevel model described above with a baseline covariate. These outcomes include Efficacy outcomes for parent and child reports of HRQOL, parent distress, child depression, and child peer victimization. A second set of outcomes involve tests of treatment condition differences where a baseline covariate is not available. These outcomes will be analyzed similarly with a multilevel model, however there will not be a level-1 covariate for the outcome at baseline. Outcomes to be analyzed in this manner include: parent and child satisfaction within Efficacy as well as attendance, participation, and cost from Implementation. The stigma outcome within Efficacy will be analyzed by comparing the proportions reporting child stigmatization between treatment conditions. This will be done for both child and parent report. A third set of outcomes will be examined descriptively. These outcomes include participation from Reach as well as descriptions of the barriers obtained in the qualitative analysis, school-level demographics from Adoption, engagement from Implementation, the number of schools retaining intervention components and summaries of factors related to maintenance from Maintenance. Participant demographics, reported food insecurities, and technological feasibility will also be examined descriptively.

Missing Data. While attrition and incomplete data may be unavoidable, the deleterious effects missing data may have on our results can be mitigated through a combination of careful data collection and thoughtful analysis. Full information maximum likelihood estimation which uses all available data to build a multidimensional likelihood function for each highest-level unit (schools) will be used for the multilevel models. For variables brought into the likelihood function, any missing cases are assumed missing at random, which means random only after conditioning on model predictors and the observed outcomes. Reasons for student departure (e.g., dropout versus changing schools) can be tracked and included as model predictors to help reduce the bias that might otherwise be created.

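### Heights and weights taken at home during school closures are not distinguished from school readings when BMI and BMIz are derived or analysed

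*Combined protocol and SAP*

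**What the plan says.** Section II.D, Primary Measures, item 2 (child BMIz and parent BMI) sets the standard method. On assessors and equipment: "Height and weight will be assessed by fully trained onsite school representatives on standardized, calibrated equipment provided by the study". Height is taken in "triplicate via a Harpenden Holtain stadiometer, Model 603". For weight: "Weight will be measured in triplicate on a portable SECA digital scale".

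Section II.C gives the contingency for closures. First, "parents will be trained on how to obtain height and weight at home". Then "Digital scales and tape measures will be sent to the families, and each family will measure the height and weight", and this is done "during a video call via Zoom app with an iAmHealthy team member to ensure measurement accuracy". The section does not say whether home readings are repeated.

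For derivation, item 2 says only: "To calculate child BMIzand parent BMI we will use standard formulas/equations". For analysis, section II.E says: "Some outcomes will be analyzed using the multilevel model described above with a baseline covariate". That model is not described in the available text. The missing-data paragraph of II.E brings all available data into the likelihood and sets no restriction by measurement method.

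Table 6 groups child BMIz and parent BMI with the primary outcomes, while the ITT text in II.E treats BMIz as a secondary hypothesis variable. Change in BMIz is also the denominator of the cost-effectiveness measure (Other Variables Assessed, Cost).

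**The concern.** The same outcome can be measured in two ways of unequal precision. The instrument, the operator and possibly the number of readings all change when a school closes, and the scale changes as well as the height device. A closure can fall between a child's baseline and follow-up. The change in that child's BMIz then contains the method difference as well as any real change. Closures affect whole schools, and schools are the unit of randomisation, so such differences are likely to be shared within clusters.

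No flag, calibration against the stadiometer or sensitivity analysis is described. The COVID-19 survey in II.D asks about the pandemic's effect on the family, not about how height and weight were measured. Without a record of method, an analyst could not later tell the two kinds of reading apart. For parents, re-measuring height at each visit adds error for no gain, because adult height is effectively constant over the study.

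**Working it through.** The documents state no figure on height error, outcome SD, ICC or power, so there is no plan figure to reproduce. All sizes below rest on assumed inputs.

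**1. From height error to BMI error.** BMI = w/h². If height is read as h + e, the relative change in BMI is (h/(h+e))² − 1, which is about −2e/h. For heights read too high:

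| True height (assumed) | e = 1 cm | e = 2 cm |
|---|---|---|
| 125 cm (child) | (125/126)² − 1 = −1.6% | (125/127)² − 1 = −3.1% |
| 145 cm (child) | (145/146)² − 1 = −1.4% | (145/147)² − 1 = −2.7% |
| 165 cm (parent) | (165/166)² − 1 = −1.2% | not computed |

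A 1 cm error at 125 cm is 0.8% of height and 1.6% of BMI: doubled, with the sign reversed. Heights read too low give slightly larger changes upward (1.62% against 1.58% at 125 cm).

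**2. On the BMIz scale.** At an assumed BMI of 20 and heights of 125-140 cm, 1 cm is 0.28-0.32 kg/m². If one BMIz unit is taken as 2-4 kg/m², that is 0.28/4 = 0.07 to 0.32/2 = 0.16 BMIz.

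**3. Effect on the arm contrast of a systematic error.** Bias = error × (difference between arms in the share of schools measured at home). The 18 schools are from section II.B; 9 per arm is assumed. With a systematic error of 0.15 BMIz:

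- 3 of 9 schools in each arm: 0.15 × 0/9 = 0
- 4 against 3: 0.15 × 1/9 = 0.017
- 6 against 3: 0.15 × 3/9 = 0.050

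**4. Effect of purely random error on power.** Take 72 children per arm (144/2), the difference set so that power is 80% without home error, and total SD = √(SD² + p × s²). Here p is the home-measured share and s the home error SD. The design effect 1 + 7 × ICC cancels, because the difference is set at the same ICC (0.01 and 0.05 give the same result).

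| Outcome SD | s | Power at p = 33% | Power at p = 100% |
|---|---|---|---|
| 0.3 | 0.08 | 79.1% | 77.2% |
| 0.3 | 0.15 | 76.8% | 70.7% |
| 0.5 | 0.08 | 79.7% | 79.0% |
| 0.5 | 0.15 | 78.8% | 76.5% |

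This treats errors as independent between children. It does not cover a shift shared by a whole school.

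**The case against.** The best defence is that this is an emergency contingency with real safeguards. Parents are trained, and a staff member is on the call specifically to secure accuracy. Both make errors of 1-2 cm less likely. That stands as an argument about size. It does not supply a record of method or an analysis that uses one.

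It can also be said that pooling of the two methods is inferred from silence. That is correct. The plan never says that the readings are pooled, and since the multilevel model is not described in the available text, its covariates beyond baseline cannot be checked. The point is therefore confined to the absence of any stated distinction.

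Three stronger readings are tempting and not supported:

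- A reader might infer that the height error is itself squared in BMI. Height is squared, so a small relative error is roughly doubled.
- A reader might infer that iAmHealthy families, coached toward a weight target, would measure in their own favour. No weight target is stated. Section II.A describes behavioural, nutrition and exercise topics with goal setting.
- A reader might infer that home measurement costs the trial a blinded assessor. No blinding is stated for the school representatives either.

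Finally, closures can affect both arms, and with equal home shares and equal errors the arm contrast is unaffected. That stands, although with 18 schools some chance imbalance is plausible.

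**Conclusion.** The point holds as a cheap improvement, not as a demonstrated bias. Two methods of unequal precision feed BMI and BMIz, and the available text does not distinguish them in derivation or analysis. An assumed 1 cm height error moves child BMI by 1.4-1.6% (heights of 125-145 cm) and parent BMI by 1.2% (165 cm).

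A reader might conclude that the treatment comparison is compromised. The documents do not support that: they give neither the true error nor the share of home visits, and bias needs one of these to differ by arm. Under the assumptions shown, a systematic error of 0.15 BMIz gives a bias of 0 to 0.050 BMIz. Purely random error lowers a nominal 80% power to between about 71% and just under 80%; the lowest value needs every child measured at home, the larger error SD and the smaller outcome SD.

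**What to change.** 1. Compute parent BMI at every visit from one stadiometer height per parent: baseline, or the first available. This removes home-height error from parent BMI wherever such a reading exists. It does not address the change of scale.
2. Record the measurement method for both height and weight at every reading. This belongs at collection, because it may be hard to reconstruct later.
3. Add a sensitivity analysis of child BMIz. Replace each home height by interpolation between that child's stadiometer readings where a later one exists; otherwise exclude the home reading. The monthly school visits help here, but a home reading at the final follow-up has no later value. For one at 8 months, the next scheduled height is that follow-up.

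A method covariate should not go into the main model. Home readings arise during closures, so the term would be confounded with real effects of the closure period on weight and could absorb true change.

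The cost is one data field and a little more analysis. The sensitivity analysis carries either the interpolation assumption or the loss of some readings. No figure stated in the plan changes.
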